6.6.8.1. Endometrial biopsy

Biopsies for histological assessment were obtained for each subject at the following timepoints:

- Month 6 or one at Month 12 if endometrium thickness via TVUS is > 5 mm
- Month 1 ExtFU, 3 ExtFU, or 6 ExtFU if not obtained at Month 12 or if the preceding biopsy diagnosis is different than "benign endometrium"

For biopsies with reported primary diagnosis "Hyperplasia" or "Malignant Endometrial Neoplasm" at other visits than screening, a second read of the biopsy was to be performed. If the diagnosis of the two reads was different, then the sample was to be re-read a 3rd time. In case of multiple readings, the following rules will be applied for the statistical analysis:

- If 2 readings out of 3 lead to the same diagnosis, one of these 2 records will be selected.

- Otherwise, the record corresponding to the most severe diagnosis should be selected considering the following order, from less severe to more severe: simple without Atypia hyperplasia < complex without Atypia hyperplasia < simple with atypia hyperplasia < complex with Atypia hyperplasia < other malignant neoplasm.

In addition, in order to perform a quality check of the readings, 15% of biopsies were sent blinded for a second read when the primary diagnosis was "Benign Endometrium". In case of multiple readings when the primary diagnosis from the first read is "Benign Endometrium", this first read will be used for the analysis. Biopsies with a primary diagnostic 1 "Benign Endometrium" will be analyzed in the classification "Benign Endometrium without Hyperplasia or Atypia".

A summary at each time point will be performed (number and percentage of subjects with normal, abnormal, not assessable).

Biopsy assessment will be summarized by classification (primary diagnosis 1) and primary diagnoses (diagnoses 2, 3 and 4) at each visit. Subjects will be counted only once for classification (primary diagnosis 1) and a subject could be in several diagnoses (e.g. if for example diagnoses 2 and 3 are fulfilled).

Possible results by classification (primary diagnosis 1) and primary diagnoses (diagnoses 2, 3 and 4) are:

- Benign Endometrium without Hyperplasia or Atypia: Proliferative, Atrophic, Metaplastic Changes, Secretory, Indeterminate, Inactive, Polyp, Endometritis, Menstrual phase, Other
- Hyperplasia: Simple with Atypia, Simple without Atypia, Complex with Atypia, Complex without Atypia
- Malignant Endometrial Neoplasm: Carcinoma, Sarcoma, Other Malignant.

If any diagnosis does not correspond to any on the list, the diagnosis will be coded as: Other Malignant if classification is Malignant Endometrial Neoplasm, and Other for any other classification.

Endometrial biopsy results, including multiple readings, will be reported in listings.

Due to the war situation in Ukraine, some biopsy samples may have been collected and analyzed by local laboratories. Those assessments will be flagged in the listings. Information about local biopsy assessment is reported in Data Management Close queries file. This file will be provided by data management department and reviewed by Sponsor. Biopsy assessments performed locally can be identified in the queries list from Endometrial Biopsy page, by subject and visit and by word search, with answer to query containing the word "local".

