10.2.2.1 Study visit: Month 1 Extension FU (Month 1 ExFU)

Month 1 ExFU visit should be scheduled on Day 365 ± 7 days after main study Day 1 (or 28 days ± 7 days after last IMP intake for early discontinued subjects).

The following tests and evaluations will be performed at Month 1 ExFU visit:

- eDiary completion compliance check
- ePRO completion, ideally before any other procedures or assessments: mPGIS and PPGIC (must be completed last)
- Concomitant treatments recording
- AE recording
- Completion of the paper C-SSRS questionnaire (version for “already enrolled subjects” (see Appendix S) for patients responding to the C-SSRS for the first time during the study, or version “since last study visit” (see Appendix T) for patients for whom the C-SSRS was completed at the previous study visit)
- ECG
- Vital signs (BP and heart rate)
- Urine pregnancy test and contraception dispensing and counselling
- Urinary protein dipstick
- Blood samples for haematology, coagulation parameters, chemistry, hormones (E2, LH and P4)
- Endometrial biopsy only if diagnosis at Month 12 was different than “benign endometrium” or if no endometrial biopsy was done at Month 12 (see section 10.4.5).
- Prescribe/dispense permitted analgesics as rescue medication
- Dispense calcium and vitamin D supplementation

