10.2.2.2 Study visit: Month 3 Extension FU (Month 3 ExFU)

Month 3 ExFU visit should be scheduled on Day 421 \pm 7 days after Day 1 (or 84 days \pm 7 days after last IMP intake for early discontinued subjects).

The following tests and evaluations will be performed at Month 3 ExFU Visit:

- eDiary completion compliance check
- ePRO and ClinRO completion, ideally before any other procedures or assessments: EHP-30, EQ-5D-5L, PROMIS, mPGIS, PPGIC, HRUQ, HRPQ (mPGIS and PPGIC must be completed last)
- Concomitant treatments recording
- AE recording
- Completion of the paper C-SSRS questionnaire (version for “already enrolled subjects” (see Appendix S) for patients responding to the C-SSRS for the first time during the study, or version “since last study visit” (see Appendix T) for patients for whom the C-SSRS was completed at the previous study visit)
- ECG
- Physical examination, including weight recording
- Vital signs (BP and heart rate)
- Urine pregnancy test and contraception counselling
- Gynecological examination
- Manual breast examination (by palpation)
- TVUS of uterus
- Urinary protein dipstick
- Fasting (overnight) blood samples for haematology, coagulation parameters, chemistry, lipids, hormones (E2, LH and P4) and bone markers. For subjects who do not resume menses by the Month 3 ExFU visit, an FSH test should be performed at a local laboratory and the subject should be advised to consult for gynaecological evaluation.
- Endometrial biopsy only if diagnosis at preceding biopsy was different than “benign endometrium” or if no endometrial biopsy was done at Month 12 nor at any visit after Month 12 (see section 10.4.5).
- Prescribe/dispense permitted analgesics as rescue medication
- Dispense calcium and vitamin D supplementation

10.2.2.3 Study visit: Month 6 Extension FU (Month 6 ExFU) – End of Follow-up visit

Month 6 ExFU visit should be scheduled on Day 505 \pm 7 days after Day 1 (or 168 days \pm 7 days after last IMP intake for early discontinued subjects).

The following evaluations and tests will be performed at Month 6 ExFU Visit:

- eDiary completion compliance check
- ePRO and ClinRO completion, ideally before any other procedures or assessments: EHP-30, EQ-5D-5L, PROMIS, mPGIS, PPGIC, HRUQ, HRPQ (mPGIS and PPGIC must be completed last)
- Collection and deactivation of eDiary
- Concomitant treatments recording
- AE recording

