- Completion of the paper C-SSRS questionnaire version “since last study visit” (see Appendix T) for patients for whom the C-SSRS was completed at the previous study visit.
- ECG
- Physical examination, including weight recording
- Vital signs (BP and heart rate)
- Urine pregnancy test
- TVUS of uterus
- Endometrial biopsy if no endometrial biopsy was obtained at Month 12 nor at any visit since Month 12 (see section 10.4.5). If inadequate/no tissue is available for pathology evaluation, the biopsy should be repeated as soon as possible in the following days.
- BMD assessed by DXA for femoral neck, hip and spine. This DXA can be performed \pm 10 days from the Month 6 ExFU study visit.

This visit constitutes the end of study participation except for subjects with a BMD decrease $>$ 1.5% from the main study baseline for lumbar spine and/or $>$ 2.5% for total hip. These subjects should have a repeat DXA scan 6 months later for BMD follow-up assessment.

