Appendix B. Schedule of study assessments – Follow-up Period

Schedule of study assessments – Extension Follow-up Period			
Timing ¹	M1 ExFU	M3 ExFU	M6 ExFU
Concomitant medication	X	X	X
Adverse events	X	X	X
Columbia-Suicide Severity Rating Scale	X	X	X
ECG	X	X	X
Physical examination (including weight)		X	X
Vital signs	X	X	X
Gynecological examination		X	
Manual breast examination		X	
Endometrium TVUS		X	X
Endometrial biopsy	X ²	X ²	X ²
Clinical laboratory & urinary protein dipstick	X	X ⁴	
Subject eDiary completion check	X	X	X
Subject eDiary collection and deactivation			X
EHP-30, EQ-5D-5L, PROMIS, HRUQ, HRPQ		X	X
mPGIS and PPGIC	X	X	X
BMD by DXA			X ⁵
E2, LH, P4	X	X	
FSH at local laboratory for subjects that do not resume menses at M3 ExFU visit		X	
Bone biomarkers		X	
Permitted analgesic prescribing/dispensing	X	X	
Vitamin D and calcium dispensing	X	X	
Urine pregnancy test and contraceptive dispensing and counselling	X	X	X

¹ All follow-up study visits should take place at the end of the defined period (i.e. M1 ExFU visit should be scheduled at the end of the first month of follow-up, M3 ExFU visit should be scheduled at the end of the third month of follow-up, etc.). A month is defined as 28 days/4 weeks. Visits should be scheduled \pm 7 days from the calculated date.

² Endometrium biopsy will be taken only if diagnosis at preceding visit was different than “benign endometrium” or if no endometrial biopsy was done at M12 nor at any visit since M12.

³ An end-of-study biopsy is mandatory if no endometrium biopsy was obtained at M12 nor at any of the subsequent visits.

⁴ Overnight fasting is required.

⁵ Subjects with a BMD decrease from main study baseline of > 1.5% for lumbar spine and/or > 2.5% for total hip at M6 ExFU visit will have an additional DXA scan 6 months later.

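### Endometrial biopsy results are planned only as visit-wise percentages of different, partly result-selected subsets; a per-woman worst-diagnosis table is missing

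*SAP*

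**What the plan says.** The safety endpoint in Protocol 7.2 and SAP 3.3 is any pathological endometrial change from baseline on histology. SAP 6.6.8.1 serves it with two summaries. One gives "number and percentage of subjects with normal, abnormal, not assessable" at each time point. The next sentence, from which any hyperplasia percentage would come, tabulates classification and diagnosis at each visit. Neither states a denominator. The section plans no summary across visits and no shift from baseline; individual results go to listings.

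Who is biopsied differs by visit:

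- **Month 12.** SAP 6.6.8.1: "Month 6 or one at Month 12 if endometrium thickness via TVUS is > 5 mm". Protocol 10.2.1.5 and 10.4.5 give the same threshold.
- **Follow-up, SAP 6.6.8.1.** "Month 1 ExtFU, 3 ExtFU, or 6 ExtFU if not obtained at Month 12 or if the preceding biopsy diagnosis is different than" benign endometrium.
- **Month 1 ExFU, Protocol 10.2.2.1.** A Month 12 diagnosis other than benign, "or if no endometrial biopsy was done at Month 12".
- **Month 3 ExFU, Protocol 10.2.2.2.** A preceding diagnosis other than benign, or "if no endometrial biopsy was done at Month 12 nor at any visit after Month 12".
- **Month 6 ExFU, Protocol 10.2.2.3.** "Endometrial biopsy if no endometrial biopsy was obtained at Month 12 nor at any visit since Month 12"; no route for a non-benign preceding result. Footnote 2 of Appendix B, which covers all three follow-up visits, does have that route: "Endometrium biopsy will be taken only if diagnosis at preceding visit was different than" benign endometrium, or no biopsy yet. The SAP has it too.

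SAP 5.5 assigns unscheduled and early-discontinuation safety assessments to a visit only if they fall within 14 days of the theoretical date of a visit where that assessment was planned, and only if that visit or window has no other assessment.

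**The concern.** A table with one row per visit invites reading down the column. Here the rows are different women. Month 12 describes thicker endometria. Month 1 ExFU describes mostly the women skipped at Month 12, plus repeats of non-benign results. Month 3 ExFU is made up of repeats and stragglers. A woman with a benign Month 12 biopsy is not scheduled again, while a woman with a non-benign one returns and may be counted in several rows.

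The safety question is how many treated women had endometrial pathology on histology. No visit row estimates that, and the rows cannot be added because of the repeats. A reader could see a false trend in either direction after treatment stops.

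**Working it through.** **Cohort size.** Protocol 13.2: 450 × 0.80 × 0.80 = 288, which reproduces the planned entry number. The documents give no biopsy or hyperplasia rate, so everything below is illustration.

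**Assumptions, with ranges.** N = 288; f = share biopsied at Month 12 (30, 50, 80%); h = hyperplasias found at Month 12 (1 or 3); s = chance that a hyperplasia is still present at the next biopsy (0, 0.5, 1); q = hyperplasia rate among women not biopsied at Month 12 (0, 0.5, 1%). Hyperplasia is the only non-benign result. The denominator is women biopsied at the visit. SAP 6.2.1 (non-missing values) and Protocol 13.5 (subjects assessed at the time point) point to that denominator, but SAP 6.6.8.1 does not state it.

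**Formulas.** B = f·N and U = N − B.

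- Month 12: h/B
- Month 1 ExFU: (s·h + q·U)/(h + U)
- Month 3 ExFU, if everyone eligible was biopsied at Month 1: s, because everyone left was selected on a non-benign result
- Per woman: (h + q·U)/N

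**Results for h = 3, s = 1, q = 0.**

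| f | Month 12 | Month 1 ExFU | Month 3 ExFU | Per woman |
|---|---|---|---|---|
| 80% | 3/230 = 1.30% | 3/61 = 4.92% | 3/3 = 100% | 3/288 = 1.04% |
| 50% | 3/144 = 2.08% | 3/147 = 2.04% | 3/3 = 100% | 3/288 = 1.04% |
| 30% | 3/86 = 3.49% | 3/205 = 1.46% | 3/3 = 100% | 3/288 = 1.04% |

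**Direction from Month 12 to Month 1 ExFU.** With q = 0, a rise needs s > (h + U)/B. For h = 3 the threshold is 61/230 = 0.27 at f = 80%, 89/202 = 0.44 at 70% and 118/173 = 0.68 at 60%. At 50% it is 147/144 = 1.02, so no rise is possible. With s = 0 and q = 0 the Month 1 figure is 0%. Over all 54 combinations (3 × 2 × 3 × 3) the percentage rose in 23 and did not rise in 31; a rise occurred in 2 of 18 at f = 30%, 7 of 18 at 50% and 14 of 18 at 80%. These counts describe the grid and are not probabilities.

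**Month 3 ExFU with m women still unbiopsied** (h = 3, q = 0): s²·h/(s·h + m). For m = 6 this is 3/9 = 33% at s = 1, 0.75/7.5 = 10% at s = 0.5, and 0% at s = 0. For m = 12 it is 3/15 = 20% and 0.75/13.5 = 5.6% at s = 1 and 0.5.

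**Other denominator.** If the whole analysis set were used, the first scenario would show 3/288 = 1.04% in every row. The inflation would vanish, but the same three women would be counted three times and unbiopsied women would count as free of pathology.

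**Biopsies outside the rows.** Within extension treatment, biopsy is planned only at Month 6 (Day 169) and Month 12 (Day 337). The 14-day windows reach Day 183 and start again at Day 323. Days 184 to 322, that is 139 days, belong to neither. A withdrawal biopsy at about Month 9 (Day 253) is 84 days from both planned visits. A later repeat may put that woman in a follow-up row, but the result that prompted it would not be in a visit row.

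**The case against.** A reader might infer that the hyperplasia percentage must rise after Month 12 because abnormal results are re-biopsied. The documents do not support that. Month 1 ExFU also takes in every woman not biopsied at Month 12, which can dilute the percentage, and a hyperplasia that has resolved counts as benign at the repeat. A steady rise needs persistence together with a hyperplasia rate in thin endometria close to that in thick ones, or a large share biopsied at Month 12. At Month 6 ExFU, Protocol 10.2.2.3 gives no result-selected route at all; only Appendix B and the SAP do.

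A reader might also infer that no planned table counts women with pathology. That goes too far. Under Protocol 12.1.2, objective abnormalities judged clinically significant are reportable as adverse events, and SAP 6.6.1 counts each woman once by system organ class and preferred term, including over combined extension treatment and follow-up. These tables depend on investigator reporting and have no biopsied-women denominator, so they do not replace a histology summary.

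It is fair to add that counts accompany the percentages, that late rows will hold few women over four treatment groups, and that every reading is listed. An attentive reader would not take 3 of 3 at face value. This limits the harm but does not supply the missing figure. Dropping percentages from follow-up rows would be only a presentation preference, and I do not ask for it.

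**Conclusion.** The concern holds in a limited form. The visit percentages describe different, partly result-selected subsets, are not comparable over time, and do not estimate the proportion of treated women with endometrial pathology. The Month 3 ExFU row can be strongly inflated: in the illustration it ranges from 0% to 100% against 1.04% per woman, depending on persistence and on how many women are still unbiopsied. That inflation needs persisting abnormal results and a denominator of women biopsied at the visit, which the general rules imply but SAP 6.6.8.1 leaves unsaid. The direction from Month 12 to Month 1 ExFU is not fixed.

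Two findings need no assumed rates. SAP 6.6.8.1 plans no per-woman summary for a per-woman safety endpoint, and SAP 5.5 leaves for-cause and withdrawal biopsies from most of the treatment period outside every visit row. The SAP already uses per-subject summaries elsewhere, such as the worst on-treatment liver value and progesterone above threshold at least once (6.6.3), so the biopsy section is out of step with its own practice.

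**What to change.** 1. Add one table by treatment group on the Extension Safety Analysis Set: each woman's worst diagnosis over all biopsies (scheduled, unscheduled and withdrawal) after the first extension dose through Month 6 ExFU. The denominator is women with at least one assessable biopsy; show the number with none beside it. The severity order that SAP 6.6.8.1 already gives for discordant readings can be reused, with benign placed below it.
2. State the denominator of each visit row, and in follow-up rows show the reason for biopsy: not done at Month 12, or repeat after a non-benign result.
3. Reconcile the Month 6 ExFU biopsy criteria in Protocol 10.2.2.3, Appendix B footnote 2 and SAP 6.6.8.1. I take no position on which is right.

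The cost is one extra table and a column or footnote in the existing ones, all from data already collected.

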6.6.8.2. Gynecological and Breast examination

Gynecological Examination was to be assessed at Month 6, Month 9 and Month 12, as well as Month 3 of the extension Follow-Up period.

Breast examination (by palpation) was to be performed at Month 6 and Month 12, as well as Month 3 of the extension Follow-Up period.

A summary at each time point will be performed (number and percentage of subjects with normal, abnormal significant) for Gynecological and Breast Examinations.

Results will also be reported in listings.

6.6.8.3. PAP Smear

PAP Smear is collected at Screening. A listing of abnormality information and a listing of diagnosis results will be provided, including possible unscheduled assessments.

6.6.8.4. Columbia-Suicide Severity Rating Scale (C-SSRS)

The C-SSRS questionnaire prospectively assess the occurrence of treatment-emergent suicidal ideation and behavior.

Subjects completed:

- either the "Baseline" C-SSRS version, capturing lifetime history of suicidal ideation and behavior, for subjects who were still in screening period in the main study,

- or the "already enrolled subjects" C-SSRS version, for subjects already enrolled in the main or in the Extension study, and who were providing answers to the C-SSRS for the first time during the study

- the "since last study visit" C-SSRS version, dedicated to subjects for whom the C-SSRS was completed at the previous study visit, for use at all remaining study visits.

The "Baseline" C-SSRS version was to be completed during Screening, or at Day 1 if not done during Screening.

The number of subjects experiencing the following, at baseline and at any time post-baseline in the extension study, will be summarized for each month from Day 1 to Month 12 and from Month 6 up to Month 12. For Month 6 to Month 12 period, the "since study start" questions from already enrolled questionnaire will not be included, as it cannot be identify whether the event occurred between Day 1 and Month 6 or Month 6 and Month 12.

- Any suicidal ideation or behavior
 - Wish to be dead.
 - Non-specific active suicidal thoughts.
 - Active suicidal ideation with any methods (not plan) without intent to act.
 - Active suicidal ideation with some intent to act, without specific plan.
 - Active suicidal ideation with specific plan and intent.
- Any Suicidal Behavior
 - Actual attempt.

Page 71 of 99

CRS-BS-TP-000005 V 2.0

- Interrupted attempt.
- Aborted attempt.
- Preparatory acts or behavior.
- Completed suicide (Actual attempt leading to death) (not at baseline)
- Emergence of suicidal ideation.
- Worsening of suicidal ideation.
- Emergence of suicidal behavior.

Any suicidal ideation or behavior is defined as an answer "Yes" for at least one of five questions for suicidal ideation or for at least one of five questions for suicidal behavior.

Emergence of suicidal ideation/behavior is defined as having no suicidal ideation/behavior at baseline and having reported any type of suicidal ideation/behavior at any time post-baseline (including "Since Study Start" answers).

Worsening of suicidal ideation is defined to occur when the most severe suicidal ideation rating since study start at any time post-baseline is more severe than its rating at baseline. The Suicidal ideation rating is defined as the following, as recommended in the C-SSRS scoring and analysis guide in https://cssrs.columbia.edu/wp-content/uploads/ScoringandDataAnalysisGuide-for-Clinical-Trials-1.pdf:

Maximal suicidal ideation category during the period (baseline, post-baseline up to Month 12 FU period) where categories range from 0 to 5:

- 0. No ideation
- 1. Wish to be dead
- 2. Non-specific active suicidal thoughts.
- 3. Active suicidal ideation with any methods (not plan) without intent to act.
- 4. Active suicidal ideation with some intent to act, without specific plan.
- 5. Active suicidal ideation with specific plan and intent.

If data of suicidal ideation or behavior is missing at baseline then the subject will not be included in summaries of emergence or worsening of suicidal ideation or behavior. The "already enrolled subjects" C-SSRS version ("Prior to Entry Study") will be used as baseline for subjects already randomized at the time of C-SSRS questionnaire implementation.

Same analysis will be repeated on the extension follow-up period (from Month 1 to Month 6 of the Extension FU Period).

6.6.8.5. Time to the first post-treatment menses

The first post-treatment menses will be defined from the Vaginal Bleeding daily ediary, as the first day for which the subject recorded bleeding after the last treatment administration date of the extension study, i.e., the first day with "BLEEDING" or "HEAVY BLEEDING" after the last treatment administration date of the extension study.

Time to first post-treatment menses is defined as:

Time to first post-treatment menses (days) = (day of first post-treatment menses – last treatment administration date in extension) + 1

Only data from the follow-up extension period will be included, and the analysis will be provided on the Follow-up Extension Safety Analysis Set, by treatment group.

Subjects who have not recorded any bleeding up to the end of the follow-up extension period will be considered as right-censored data at the last ediary vaginal bleeding record date before the end of the extension follow-up period (as defined in section 5.2) with time of censoring = last non-missing ediary vaginal bleeding record date – last treatment administration date in extension +1.

The probability of subjects having bleeding will be displayed by treatment group in the form of cumulative probability curves estimated using the non-parametric Kaplan-Meier method. Point estimates and corresponding 2-sided 95% CIs using the Greenwood's variance estimate will be provided at 28 days, 56 days, 84 days, 112 days, 140 days, 168 days, 196 days after the last treatment administration date in extension. Percentiles (25th, 50th, and 75th) and corresponding 2-sided 95% CIs will also be provided; "N/A" will be presented for any of the percentiles not reached.

Subjects with or without first post-treatment menses, time to first post-treatment menses, end of study status and end of study date will be presented in a by-subject listing.

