10.6.3 Non-Drug Therapies

Contraceptive use:

For subjects of childbearing potential and requiring contraception, non-hormonal contraception is required until 3 months after the end of treatment. Two forms of non-hormonal contraception will be required e.g. condom with spermicide (if in the opinion of the Investigator a woman is at risk of acquiring HIV, spermicide should be avoided; condom with diaphragm may be used). Suitable condoms with spermicide will be provided free of charge to subjects over the duration of the study.

Contraception is still required from 3 months after the end of the Treatment Period until the end of the post-treatment Follow-up Period; hormonal contraception is allowed.

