5.2. Data Conventions

5.2.1. Last extension treatment administration date, End of extension Study date and Period definitions

The last extension treatment administration date will be defined as the date from the treatment termination reported in the extension period eCRF page. If this date is missing, the last date with a drug intake in the eDiary that is inferior or equal to Month 12 visit or the last available date with a drug intake in the eDiary if the subject discontinued the extension treatment will be used.

For subjects who entered the extension, the end of the extension study date will be the last assessment date in the extension study defined as last assessment recorded in the eCRF (excluding end date of adverse events and concomitant medications) or ediary date (excluding drug intakes recorded after last extension treatment administration date). This will not necessarily be the same date as last assessment date as recorded in the eCRF.

For each 28-day period prior to Month X (except Month 12), the end of the period will be defined as the Month X visit date. If subject discontinued prior to Month X, the end of the period will be the date from the treatment termination of extension period eCRF page or the last date with a drug intake in the eDiary if missing. If the subject missed the Month X visit (but did not discontinue), the subject might still have filled the diary during that time: the theoretical Month X date will be used to define the end of the 28-day period. The theoretical Month X is defined with respect to Day 1 as Month X= Day 1+ $28^{*}X$.

For the 28-day period prior to Month 12, the end of the period will be defined as the last extension treatment administration date.

Note:

For Adverse Events, Concomitant Medications and Daily diaries data collected on the Month 6 date will be part of the extension for subjects entering the extension study.

For Adverse Events, Concomitant Medications and Daily diaries, data collected on the Month 12 date will be part of the Extension Follow-up period for subjects entering the Extension follow-up period.

The extension treatment period will be defined as Month 6 up to (Month 12 date -1) or treatment discontinuation date.

The extension follow-up period will be defined as the Month 12 date or (treatment discontinuation date+1) up to the extension follow-up end date (for subjects who entered the extension follow-up).

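### Time to first post-treatment menses counts a bleed already in progress at the last dose as an event at 2 days

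*SAP*

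**What the plan says.** SAP 6.6.8.5 takes the event from the daily bleeding diary, "as the first day for which the subject recorded bleeding after the last treatment administration date of the extension study", and then narrows it to "the first day with 'BLEEDING' or 'HEAVY BLEEDING' after the last treatment administration date of the extension study". Spotting is a separate diary category (Protocol 10.3.1.3) and does not count. The time is "day of first post-treatment menses – last treatment administration date in extension) + 1". The section sets no bleed-free interval and no new-onset requirement, and it makes no exception for women bleeding on the last dose day.

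Only diary data from the follow-up period are used. SAP 5.2.1 opens that period at once: "The extension follow-up period will be defined as the Month 12 date or (treatment discontinuation date+1".

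There is one censoring rule: "Subjects who have not recorded any bleeding up to the end of the follow-up extension period will be considered as right-censored data", at the last bleeding-diary record. Results are shown by treatment group as "cumulative probability curves estimated using the non-parametric Kaplan-Meier method", with quartiles and with estimates at "28 days, 56 days, 84 days, 112 days, 140 days, 168 days, 196 days after the last treatment administration date".

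Protocol 10.6.2 bars hormonal contraception until 3 months after the end of treatment. From then "until the end of the post-treatment Follow-up Period; hormonal contraception is allowed" (Protocol 10.6.3). SAP 6.6.8.5 does not mention hormone use.

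**The concern.** The endpoint is named as time to the first menses after treatment. A bleed that began on treatment and runs past the last dose is not a post-treatment onset, yet it enters the curve as the earliest possible event. Such bleeding is foreseeable, because Protocol 5.5.3 lists menstrual-cycle disturbances, including metrorrhagia, among the expected effects of linzagolix. The error runs one way and makes return look faster.

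It can also set two safety outputs against each other. Protocol 10.2.2.2 asks for an FSH test in women whose menses have not resumed by the Month 3 follow-up visit, and SAP 6.6.3 summarizes the results. A woman with a carry-over bleed and no bleeding afterwards could appear in that FSH table while the Kaplan-Meier curve shows her as resumed at day 2.

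The later part of the curve raises a smaller question. A woman still without menses at about 3 months may start a hormonal method. The method may suppress bleeding, leaving her at risk without an event, or it may produce a withdrawal bleed that counts as one. Neither outcome describes natural return.

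**Working it through.** The plan gives no expected value, rate or sample size for this endpoint, so there is no figure to reproduce. The dates below come from the documents. The rates are assumptions.

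**1. The 2-day score.** Month 12 is Day 337 (Protocol 10.2), and the last dose is planned for the day before, Day 336 (Protocol 10.2.1). The follow-up data open on Day 337. For a bleed that continues into that day, T = (337 − 336) + 1 = 2. For a woman who discontinues on day d, T = ((d + 1) − d) + 1 = 2. Two days is also the smallest value the formula can give.

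**2. Effect on the early estimates.** Let c be the share of women bleeding across the last dose and F(t) the distribution of true return. From day 2 onward the SAP curve is c + (1 − c)·F(t). Assume F is lognormal with median 35 days and log-SD 0.5. Then F(28) = Φ(ln(28/35)/0.5) = Φ(−0.446) = 0.328. At c = 10%, 0.10 + 0.90 × 0.328 = 0.395. Simulation with 400,000 women per scenario gives:

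| Assumed c | 28-day probability | 25th percentile | Median |
|---|---|---|---|
| 0% | 32.8% | 25 days | 35 days |
| 5% | 36.2% | 24 days | 34 days |
| 10% | 39.5% | 22 days | 33 days |
| 20% | 46.3% | 17 days | 30 days |
| 30% | 53.0% | 2 days | 27 days |

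Once c exceeds 25%, the 25th percentile is 2 days whatever F is.

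**3. Which time points hormone use can reach.** With the protocol's 28-day month, 3 months is 3 × 28 = 84 days. Month 6 follow-up is Day 505, so T = (505 − 336) + 1 = 170, or 177 at the end of the +7-day window. For early discontinuers it is 168 ± 7 days after the last intake, so at most 168 + 7 + 1 = 176. The exposed estimates are therefore those at 112, 140 and 168 days. The 196-day point lies beyond scheduled follow-up.

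**4. Possible size of the hormone effect.** Assume that half of the women still without menses start a method at about day 85. Assume lognormal return with median and log-SD of 35 and 0.5, 45 and 0.6, or 55 and 0.7. The 168-day probabilities are:

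| Not back by day 84 | Natural return | SAP rule, bleeding suppressed | SAP rule, withdrawal bleed counted | Censored at start |
|---|---|---|---|---|
| 4% | 99.9% | 98.0% | 100.0% | 99.9% |
| 15% | 98.6% | 92.0% | 99.3% | 98.6% |
| 27% | 94.5% | 83.9% | 97.2% | 94.4% |

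No estimate up to day 84 changes in any row. The last column agrees with natural return only because starting a method was simulated as unrelated to return time.

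**The case against.** The strongest reply is that this is one descriptive safety endpoint with no hypothesis test, that the size is unknown, and that the low end of the assumed range is trivial: 5% carry-over moves the median by one day. That stands, and it limits the weight of the point. It does not make the definition right.

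A second reply is that the documents nowhere say the endpoint measures recovery from suppression. Protocol 5.5.3 also describes estradiol suppression at 75 mg as only partial, so a bleed across the stop date may be genuine menses. That is possible. But such a bleed began on treatment, and the time from the last dose to a day in mid-episode is not a time to post-treatment menses.

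A third reply is that the listings expose the problem. Time to menses is listed by subject, and so are concomitant medications (SAP 6.6.6). A 2-day event would be visible, but that listing is not specified to show bleeding status at the last dose or the date of hormone start, and no listing corrects the curve.

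On contraception, censoring at hormone start has a weakness of its own. Women without menses at Month 3 are advised to seek gynaecological evaluation (Protocol 10.2.2.2), so starting a method may be related to delayed return and the censoring may be informative. That stands, and it is why the analysis belongs among the sensitivity analyses.

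**Conclusion.** The event definition should be corrected. As written, BLEEDING or HEAVY BLEEDING carried across the last dose is scored as return at 2 days. This biases the 28-day probability, the 25th percentile and the median toward faster return. The direction follows from the text. The size depends on the share of women bleeding across the stop date, which the documents do not give. Under the assumptions above, the 28-day probability rises by 3 to 20 percentage points for carry-over of 5% to 30%.

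The contraception point is secondary. It concerns only women still without menses when they start a method, it can act in either direction, and it is small if few such women remain.

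A reader might infer more than the documents support:

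- That any bleeding after the last dose is an event. Spotting is excluded.
- That every event or censoring after day 84 in a contraceptive user is uninformative. A woman who bled before starting the method is unaffected.
- That four of the seven time points are compromised. The 196-day point lies outside scheduled follow-up, which leaves three.
- That the comparison between doses is biased. That would need carry-over rates to differ by arm, and no such rates are given.

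**What to change.** In SAP 6.6.8.5, count only an episode of BLEEDING or HEAVY BLEEDING that starts after the last extension dose and follows at least a pre-stated number of days with neither category. Allow on-treatment diary days to be used in checking that interval, since the section now restricts the data to the follow-up period, and say how missing diary days in it are treated. Keep the current definition as a sensitivity analysis.

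Add a second sensitivity analysis that censors women still without menses at the start of hormonal contraception as recorded in the eCRF, with a note that this censoring may be informative. It bears on the 112-, 140- and 168-day estimates.

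The cost is a few SAP sentences and two extra sets of output. Daily bleeding is already in the eDiary, and concomitant medications are recorded for the whole study (Protocol 10.6). The price is slightly later event times and a few more censored subjects. No visit, data item or aspect of care changes.
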